## **7 STUDY PROCEDURES**

Participants will have study specific assessments, undertaken at additional visits at day 1, week 4, week 6, week 8, week 12 and week 24, in addition to self-directed treatment with Alpha-Stim AID CES for a minimum of 6 weeks and a maximum of 12 weeks.

Whilst enrolled in the study, participants will be on the waiting list for high intensity psychological therapy intervention, and may begin to receive such interventions if clinically indicated following the minimum 6 - 8 week waiting period. Scores from assessments undertaken for the purposes of this study will be available to the IAPT service and may be used to inform treatment plans.

### **7.1 Participant Identification**

Eligible participants will be known to the IAPT service, as these patients will have been indicated for step three high intensity psychological therapy intervention, and will be on the waiting list. As per standard care, during step two low intensity psychological therapy intervention, as provided by the PWP or Cognitive Behavioural Therapist within the IAPT service, patients will be assessed. Those who have not improved as a result of treatment (due to a GAD-7 score remaining at 10 or above and therefore remaining to be moderate-to-severe) will be contacted by the routine PWP or Cognitive Behavioural Therapist at a face-to-face visit, via telephone, via email and/or via letter to discuss a step-up to step three therapy intervention.

As such, all PWPs and Cognitive Behavioural Therapists in the IAPT service will screen their patient lists proactively to maintain an awareness of those patients who are eligible. Concurrently to receiving information about a step-up to step three therapy intervention, patients will receive a Participant Information Sheet (PIS) to introduce and explain the study. As such, the initial approach will be from a member of the patient's routine healthcare team. Patients must respond to the PWP or Cognitive Behavioural Therapist to advise that they do

not wish to be placed on to the waiting list for step three. For any patients that are currently on the waiting list, the PWP or Cognitive Behavioural Therapist will contact the patient with a Participant Information Sheet (PIS) to introduce and explain the study.

The PIS will encourage patients that are interested in learning more about this study to contact the research nurse assigned to study delivery, by telephone, email or post. The research nurse will be employed by NIHR CRN East Midlands to assist with study delivery. Patients that do not respond will be deemed uninterested in study participation. The PWP or Cognitive Behavioural Therapist will maintain a screening log to record those patients who have been approached about study participation. The research nurse will therefore have no contact with any patient who has not indicated consent to discuss the study, and as such, no access to personal identifiable information prior to the patient themselves making contact.

No participants will be identified at any other services other than via the three teams comprising Leicestershire and Rutland IAPT service. No participants will be identified via Participant Identification Centres (PICs) and no participants will have the opportunity to self-refer as none will be recruited by publicity.

## **7.2 Consent**

Following the initial approach, and once a patient has contacted the research nurse to learn more about the study, a baseline visit will be arranged for the patient to further discuss the study and consent. The baseline visit will be an additional visit, and will take place at routine facilities used by the IAPT service (either a GP clinic room or community venue).

Patients will have the opportunity to discuss the details of the study with the research nurse, and if happy to proceed, will sign the Informed Consent Form (ICF). If a patient would not like to participate following a discussion of the study with the research nurse, their involvement will terminate at this time point and they will continue to receive routine care. The research nurse will evaluate the capacity of the patient to consent at this time point. Should the research nurse not be content that the patient fully understands the study, and is therefore able to make an informed decision regarding participation, then the patient will not be enrolled.

One copy of the ICF will be received by the participant, one copy will be stored in the Investigator Site File (ISF) and one copy will be scanned into PCMIS - the electronic patient record system used locally.

It will be made clear that all participants will continue to receive standard care assessment, as undertaken by the NHS IAPT service, standard care high intensity psychological therapy intervention as clinically indicated and provided by the NHS IAPT service, and standard care pharmacological treatment as prescribed by the participant's GP. Participation in this study will not influence nor compromise standard care treatment – all study procedures are additional to standard care. Participation in the study will have no impact upon the duration of the waiting time for high intensity psychological therapy intervention.

## **7.3 Screening**

Participants will have a confirmed working diagnosis of moderate-to-severe GAD via a GAD-7 score of 10 or more upon identification by the PWP or Cognitive Behavioural Therapist as potentially eligible for the study.

Once the ICF has been signed, the research nurse will take a urine pregnancy dipstick test for any female participant of child-bearing potential. Should the result be positive, their involvement will terminate at this time-point and they will continue to receive routine care.

It is possible that, over the timeframe of having been identified and provided consent to participate, the GAD-7 score of the participant may have changed. As such, once the ICF has been signed, the research nurse, trained in the administration of the GAD-7, will undertake a GAD-7 assessment with the participant. Should the participant, at this baseline visit, have a score of 9 or less, their involvement will terminate at this time point and they will

continue to receive routine care. The research nurse will also re-confirm full eligibility in accordance with the inclusion/exclusion criteria.

This baseline visit will be the sole additional in-clinic visit, with all other study visits undertaken via telephone. Patients that attend this baseline visit will have their travel expenses reimbursed up to a maximum of £10.00 and must submit their receipt(s) or indication of miles driven (reimbursement up to £0.45 per mile in accordance with HMRC guidance). Patients will receive this reimbursement in cash at the baseline visit.

#### **7.4 Baseline assessments**

##### **Baseline visit 1: Day 1**

Having provided consent for participation, the research nurse will notify the participant's GP via a notification letter unless the participant expressly requests that the GP is not notified, and the research nurse will undertake the following assessments:

##### Urine pregnancy test

The first assessment will be a urine pregnancy dipstick human chorionic gonadotropin test will be used to assess pregnancy in all females of child-bearing potential. The urine and dipstick will be disposed of in accordance with the Human Tissue Authority code of conduct.

##### GAD-7

*See Appendix A*

The second assessment will be the GAD-7, which is a participant-reported screening tool and severity measure for generalised anxiety disorder (GAD). The GAD-7 score is calculated by assigning scores of 0, 1, 2 and 3, to the responses categories of "not at all", "several days", "more than half the days" and "nearly every day", respectively to 7 problems over the last 2 weeks, and adding together the scores for the 7 problems. The maximum score is 21. Scores of 5, 10 and 15 are taken as the cut-off points for mild, moderate and severe anxiety.

The research nurse will administer the GAD-7 and record the data either directly into the electronic patient record (PCMIS) if available (and therefore the PCMIS record will act as source data), or into a Case Report Form (CRF) if not available (and therefore the CRF will act as source data) and then transpose the data into PCMIS or scan the CRF into the electronic file.

It is anticipated that this assessment will take approximately 5 minutes.

##### Client Service Receipt Inventory (CSRI)

*See Appendix B*

The CSRI, for use for anxiety disorders in primary care and community settings, is a measure of the full health and social care cost and patient cost of treatment.

The research nurse will administer the CSRI and record the data either directly into the electronic patient record (PCMIS) if available (and therefore the PCMIS record will act as source data), or into a Case Report Form (CRF) if not available (and therefore the CRF will act as source data) and then transpose the data into PCMIS or scan the CRF into the electronic file.

It is anticipated that this assessment will take approximately 15 minutes.

### EQ-5D-5L

*See Appendix C*

The EQ-5D-5L is a participant-reported measure of health utility and quality of life used by NICE to generate QALYs for cost effectiveness assessments. The EQ-5D-5L uses 6 items, covering the categories of mobility, self-care, usual activities, pain/discomfort, anxiety/depression and a visual analogue score of health state.

The research nurse will administer the EQ-5D-5L and record the data either directly into the electronic patient record (PCMIS) if available (and therefore the PCMIS record will act as source data), or into a Case Report Form (CRF) if not available (and therefore the CRF will act as source data) and then transpose the data into PCMIS or scan the CRF into the electronic file.

It is anticipated that this assessment will take approximately 5 minutes.

### Work and Social Adjustment Scale (WASA)

*See Appendix D*

WASA scale is a participant-reported measure of work and social function. The WASA scale uses 5 items, covering the categories of work, home management, social leisure activities, private leisure activities, and family and relationships, to the response categories of “not at all”, “slightly”, “definitely”, “markedly”, “very severely”. The maximum score is 40.

The research nurse will administer the WASA and record the data either directly into the electronic patient record (PCMIS) if available (and therefore the PCMIS record will act as source data), or into a Case Report Form (CRF) if not available (and therefore the CRF will act as source data) and then transpose the data into PCMIS or scan the CRF into the electronic file.

It is anticipated that this assessment will take approximately 5 minutes.

### PHQ-9

*See Appendix E*

The PHQ-9 is a participant-reported measure of depressive symptomatology. The PHQ-9 uses 9 items, to the response categories of “not at all”, “several days”, “more than half the days”, and “nearly every day”. The maximum score is 27.

The research nurse will administer the PHQ-9 and record the data either directly into the electronic patient record (PCMIS) if available (and therefore the PCMIS record will act as source data), or into a Case Report Form (CRF) if not available (and therefore the CRF will act as source data) and then transpose the data into PCMIS or scan the CRF into the electronic file.

It is anticipated that this assessment will take approximately 5 minutes.

### Athens Insomnia Scale

*See Appendix F*

The Athens Insomnia Scale is a participant-reported measure of sleep difficulty. Athens scale used 8 items, covering the categories of sleep induction, awakening during the night, final awakening earlier than desired, total sleep duration, overall quality of sleep, sense of well-being during the day, functioning (physical and mental) during the day, and sleepiness during the day, to 5 response categories. The maximum score is 24.

The research nurse will administer the Athens scale and record the data either directly into the electronic patient record (PCMIS) if available (and therefore the PCMIS record will act as source data), or into a Case Report Form (CRF) if not available (and therefore the CRF will act as source data) and then transpose the data into PCMIS or scan the CRF into the electronic file.

It is anticipated that this assessment will take approximately 5 minutes.

### Alpha-Stim AID CES treatment

Participants will be trained in the use of the Alpha-STIM AID medical device by the research nurse, and will be informed that they are expected to undertake 60-minute self-directed Alpha-Stim AID CES treatment sessions undertaken at their home, on a daily basis for 6 weeks. It is expected that participants will use the device in the morning if possible. Participants will receive a written instruction sheet and will be advised to contact the research nurse if they have any queries. Participants will use ear clip electrodes with the current set at their level of comfort.

Participants will undertake all sessions at home, and none in-clinic. Immediately prior to treatment, and post treatment, participants will record their level of anxiety of a scale of 0 – 10 (with 0 indicating no anxiety and 10 maximum anxiety). Participants will record these measurements in a log, which will act as source data.

*See Appendix G.*

The first treatment session should be completed after the baseline assessments undertaken by the research nurse.

During this 6-week period, participants will be on the waiting list for high intensity psychological therapy intervention.

Following 6 weeks of Alpha-Stim AID CES treatment, participants have the option to receive a further 6 weeks of treatment, which is likely to coincide with start of high intensity psychological therapy intervention as clinically indicated.

Following a maximum of 12 weeks' treatment with Alpha-Stim AID CES, all participants will cease to receive treatment on study.

## **7.5 Study assessments**

At baseline, participants will agree with the research nurse a convenient time and date for the visits undertaken via telephone. Visits should be undertaken within 5 calendar days of the exact date.

Additional visits are undertaken at 4 weeks post baseline, 6 weeks post baseline, 8 weeks post baseline, 12 weeks post baseline and 24 weeks post baseline.

### **Visit 2: Week 4 (plus or minus 5 calendar days)**

The research nurse will telephone call the participant and undertake the following assessments:

- GAD-7
- EQ-5D-5L
- WASA
- PHQ-9
- Athens Insomnia Scale
- Check treatment compliance and anxiety log completion
- Check adverse events

The research nurse will administer these and record the data either directly into the electronic patient record (PCMIS) if available (and therefore the PCMIS record will act as source data), or into a Case Report Form (CRF) if not available (and therefore the CRF will act as source data) and then transpose the data into PCMIS or scan the CRF into the electronic file.

It is anticipated that these assessments will take approximately 30 minutes in total.

**Visit 3: Week 6 (plus or minus 5 calendar days)**

The research nurse will telephone call the participant and undertake the following assessments:

- GAD-7
- EQ-5D-5L
- WASA
- PHQ-9
- Athens Insomnia Scale
- Check treatment compliance and anxiety log completion
- Check adverse events

The research nurse will administer these and record the data either directly into the electronic patient record (PCMIS) if available (and therefore the PCMIS record will act as source data), or into a Case Report Form (CRF) if not available (and therefore the CRF will act as source data) and then transpose the data into PCMIS or scan the CRF into the electronic file.

It is anticipated that these assessments will take approximately 30 minutes in total.

At this visit, the research nurse will discuss whether the participant wishes to continue with Alpha-Stim AID CES treatment in the same manner for an additional 6 weeks. If the participant does wish to do so, they will be advised that they must continue to complete the anxiety log book. The decision to continue or end treatment with Alpha-Stim AID CES will not impact upon access to stand care therapy interventions, and participants will be contacted by the IAPT service regardless of their decision at this time point. If the participant does not wish to continue with Alpha-Stim AID CES treatment, the research nurse will ask that they return the medical device via post.

The final treatment session should be completed immediately prior to the visit 3 assessments undertaken by the research nurse.

**Visit 4: Week 8 (plus or minus 5 calendar days)**

The research nurse will telephone call the participant and undertake the following assessments:

- GAD-7

- EQ-5D-5L
- WASA
- PHQ-9
- Athens Insomnia Scale
- Check treatment compliance and anxiety log completion (if continuing with Alpha-Stim AID CES treatment)
- Check adverse events (if continuing with Alpha-Stim AID CES treatment)

The research nurse will administer these and record the data either directly into the electronic patient record (PCMIS) if available (and therefore the PCMIS record will act as source data), or into a Case Report Form (CRF) if not available (and therefore the CRF will act as source data) and then transpose the data into PCMIS or scan the CRF into the electronic file.

It is anticipated that these assessments will take approximately 30 minutes in total.

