## STUDY FLOW CHART

Day 1 – Week 6 Initial Alpha-Stim AID CES treatment period with daily 60 minute sessions and pre and post anxiety scale completion.
	
Visit 1: Day 1 Baseline in clinic visit comprising informed consent, training in use of Alpha-Stim AID CES device, GAD-7, WASA, PHQ-9, EQ-5D-5L, Athens and CSRI.
	
Standard care Participant on waiting list (at least 6 - 8 weeks) for step three high intensity psychological therapy intervention, followed by assessment and at least two individual CBT sessions as required.

Week 6 – Week 12 Optional additional Alpha-Stim AID CES treatment period with daily 60 minute sessions and pre and post anxiety scale completion.
	
Visit 2: Week 4 Telephone visit comprising GAD-7, WASA, PHQ-9, EQ-5D-5L, Athens and treatment compliance and adverse events.
	

Visit 3: Week 6 Telephone visit comprising GAD-7, WASA, PHQ-9, EQ-5D-5L, Athens, CSRI and treatment compliance and adverse events. End of treatment for participants as requested.
	
Visit 4: Week 8 Telephone visit comprising GAD-7, WASA, PHQ-9, EQ-5D-5L, Athens and treatment compliance and adverse events.
	

Visit 5: Week 12 Telephone visit comprising GAD-7, WASA, PHQ-9, EQ-5D-5L, Athens and treatment compliance and adverse events. End of treatment for all participants.
	
Visit 6: Week 24 Telephone visit comprising GAD-7, WASA, PHQ-9, EQ-5D-5L, Athens and CSRI. End of study for all participants.
	

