#### **Visit 6: Week 24 (plus or minus 5 calendar days)**

The research nurse will telephone call the participant and undertake the following assessments:

- GAD-7
- EQ-5D-5L
- CSRI

- WASA
- PHQ-9
- Athens Insomnia Scale

The research nurse will administer these and record the data either directly into the electronic patient record (PCMIS) if available (and therefore the PCMIS record will act as source data), or into a Case Report Form (CRF) if not available (and therefore the CRF will act as source data) and then transpose the data into PCMIS or scan the CRF into the electronic file.

It is anticipated that these assessments will take approximately 30 minutes in total.

This is the end of study visit, after which the participant will cease communication with the research nurse.

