## 7.6 Assessment summary

ASSESSMENT	VISIT 1 DAY 1	VISIT 2 WEEK 4	VISIT 3 WEEK 6	VISIT 4 WEEK 8	VISIT 5 WEEK 12	VISIT 6 WEEK 24
CONSENT	X					
TRAINING IN USE OF ALPHA STIM AID	X					
PREGNANCY TEST	X (*)					
GAD-7	X	X	X	X	X	X
EQ-5D-5L	X	X	X	X	X	X
CSRI	X				X	X
WASA	X	X	X	X	X	X
PHQ-9	X	X	X	X	X	X
ATHENS	X	X	X	X	X	X
ALPHA-STIM AID CES TREATMENT	Ongoing	Ongoing	Ongoing (**)	Ongoing (**)	Ongoing (**)	
COMPLIANCE		X	X	X (**)	X (**)	
ADVERSE EVENTS		X	X	X (**)	X (**)	

(\*) If a female of child-bearing potential

(\*\*) If continuing with Alpha-Stim AID CES treatment between week 6 – week 12.

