## 9 SAFETY REPORTING

### 9.1 Definitions

Term	Definition
Adverse Event (AE)	Any untoward medical occurrence in a participant receiving treatment with Alpha-Stim AID CES, including occurrences which are not necessarily caused by or related to that product.
Serious Adverse Event (SAE)	A serious adverse event is any untoward medical occurrence that: 
 
• results in death
 
• is life-threatening
 
• requires inpatient hospitalisation or prolongation of existing hospitalisation
 
• results in persistent or significant disability/incapacity
 
• consists of a congenital anomaly or birth defect
 

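### Adverse-event questions reach everyone only to week 6, those continuing the device only to week 12, and no one at week 24; the flow chart omits the condition at weeks 8 and 12

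*Combined protocol and SAP*

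**What the plan says.** Section 7.5 schedules five telephone visits after baseline, and every participant receives all of them. At week 4 the list of tasks includes "Check adverse events" with no qualification, and week 6 is the same. At week 8 the line becomes "Check adverse events (if continuing with Alpha-Stim AID CES treatment", and week 12 carries the same condition. The week 24 list contains only the questionnaires and the service-receipt inventory (CSRI). It has no adverse-event item, and the section adds: "This is the end of study visit, after which the participant will cease communication with the research nurse".

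The table in section 7.6 matches 7.5. Its adverse-event row is marked at weeks 4 and 6, marked with a footnote at weeks 8 and 12, and blank at week 24. The footnote reads "If continuing with Alpha-Stim AID CES treatment between week 6 – week 12".

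The study flow chart describes weeks 4, 8 and 12 in identical words: "Telephone visit comprising GAD-7, WASA, PHQ-9, EQ-5D-5L, Athens and treatment compliance and adverse events". No condition is attached. For week 24 it gives "Telephone visit comprising GAD-7, WASA, PHQ-9, EQ-5D-5L, Athens and CSRI", with no adverse-event item.

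Section 9.1 defines an adverse event as "Any untoward medical occurrence in a participant receiving treatment with Alpha-Stim AID CES", whether or not the device caused it. The serious adverse event definition has no such limit. Sections 9.2 and 9.3 require both kinds to be recorded when the research nurse learns of them, with no end date stated. Section 11.3 describes no analysis of adverse events.

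**The concern.** The calls at weeks 8, 12 and 24 take place for everyone and the full questionnaire set is completed, yet the adverse-event question is withheld from anyone off the device. Two kinds of event can be missed.

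The first is a non-serious event that starts or persists after stopping. Sections 7.5 (visits 3 and 5) place the final session directly before the assessments at that visit, so the last scheduled adverse-event question comes straight after the last session. No later scheduled question would pick up anything that follows.

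The second is narrower but closer to the device. A participant may choose at week 6 to continue and then stop before the week 8 or week 12 call. Read literally, that person is no longer continuing and is not asked, even if an event was the reason for stopping.

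The conflict with the flow chart adds a practical problem. A nurse working from the flow chart and one working from 7.5 or 7.6 would collect different data at weeks 8 and 12. A count of adverse events presented as a 24-week figure would not show how much of the 24 weeks had been asked about.

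**Working it through.** **Who is asked, by source**

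| Call | Section 7.5 | Section 7.6 | Flow chart |
|---|---|---|---|
| Week 4 | everyone | everyone | no condition |
| Week 6 | everyone | everyone | no condition |
| Week 8 | continuers only | continuers only | no condition |
| Week 12 | continuers only | continuers only | no condition |
| Week 24 | no one | no one | no one |

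The documents disagree at weeks 8 and 12 only.

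**Inputs.** Planned sample 120 (study summary). Follow-up 24 weeks (7.9). Device use 6 weeks for all, up to 12 weeks by choice (section 4). The share p who continue after week 6 is not stated, so the whole range is shown. The only related figure is in 11.1, which expects a further 20 of 120 to improve reliably because of the second course. On that expectation at least 20/120 = 17% would have to continue.

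**Assumptions.** Complete follow-up, continuers use the device to week 12, and each question covers the time since the previous one. The documents give no coverage figure, so there is none to reproduce.

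**Formulas.** Total follow-up is 120 × 24 = 2,880 participant-weeks. Covered time is 120 × (6 + 6p), covered share is (6 + 6p)/24, and the number of adverse-event contacts is 120 × (2 + 2p).

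| p continuing | Covered participant-weeks | Covered share | Contacts |
|---|---|---|---|
| 0% | 720 | 25.0% | 240 |
| 17% (20/120) | 840 | 29.2% | 280 |
| 50% | 1,080 | 37.5% | 360 |
| 75% | 1,260 | 43.8% | 420 |
| 100% | 1,440 | 50.0% | 480 |

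For one participant, the time not asked about is 24 − 6 = 18 weeks (75%) if they stop at week 6, and 24 − 12 = 12 weeks (50%) if they continue to week 12. If the schedule is followed, all of it falls after device use ends.

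**The self-selected part.** Weeks 6 to 12 in continuers make up 6p/24 of follow-up, which is 0% to 25%. As a share of covered time they are 6p/(6 + 6p), which is 0% to 50%. Weeks 0 to 6, asked of everyone, are therefore at least half of what is covered.

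**Stopping between calls.** On a literal reading, someone who continues and stops before the week 8 call was last asked at week 6, so up to 8 − 6 = 2 weeks of device use go unasked. Someone who stops between weeks 8 and 12 was last asked at week 8, so up to 12 − 8 = 4 weeks go unasked. The covered shares in the table are upper limits to that extent.

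**Effect of the change.** Asking everyone at weeks 8 and 12, as the flow chart implies, gives 120 × 12 = 1,440 participant-weeks (50%) and 120 × 4 = 480 contacts whatever p is. Adding week 24 gives 2,880 participant-weeks (100%) and 120 × 5 = 600 contacts.

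**The case against.** The best defence is that the checks span the planned period of device use: weeks 0 to 6 for all and weeks 6 to 12 for continuers. That matches an adverse-event definition tied to receiving treatment, so the uncovered 50% to 75% is off-device time and is no shortfall against the protocol's own definition. This is largely right. It still leaves the person who stops between calls, and it depends on a definition that does not say whether an event after stopping counts.

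A reader might go further and infer that the whole safety result is self-selected. The documents do not support that. Weeks 0 to 6 cover everyone, and the week 6 question falls in the same call as the decision to continue, so a participant whose bad experience leads to stopping at week 6 is asked at that point.

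A reader might also infer that later events surface only by chance. That is too strong. Events are recorded whenever the nurse learns of them, and she calls everyone at weeks 8, 12 and 24. GAD-7, PHQ-9 (including its self-harm item) and the Athens scale are repeated for all. Under 7.5 and 7.6 the CSRI at weeks 12 and 24 asks everyone about admissions and emergency visits in the previous 3 months. Two limits remain: no section routes CSRI answers to safety reporting, and the flow chart places the CSRI at week 6 in place of week 12. The gap that stands is mainly non-serious events outside these instruments.

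A third tempting inference is that the adverse-event rate is biased in the device's favour. Undercounting after stopping is plausible, but the documents give nothing to establish its direction or size. No safety objective or adverse-event analysis is written, and section 2 describes the evidence for NICE as clinical effectiveness and economic impact.

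Finally, the flow chart may be shorthand, since compliance cannot be checked once the device is returned. Yet it uses the same words for week 4, where the question is unconditional, so a user cannot tell that weeks 8 and 12 differ.

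**Conclusion.** The point holds in limited form. Scheduled adverse-event enquiry covers 25% to 50% of follow-up time, and reaches 50% only if everyone continues to week 12. This rests on the unstated continuation share and on the assumptions listed with the calculation. What goes unasked is mainly off-device time: weeks 6 to 24 in those who stop and weeks 12 to 24 in those who continue. Read literally, it also includes up to 2 or 4 weeks of device use in those who stop between calls. The flow chart contradicts 7.5 and 7.6 at weeks 8 and 12 and agrees with them at week 24.

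This is a gap in systematic questioning and does not bar recording. It leaves the GAD-7 outcomes untouched. It should be corrected because the calls already take place and any adverse-event tally for 24 weeks would otherwise lack a clear denominator.

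**What to change.** - In 7.5, delete the bracketed condition from the adverse-event line at visits 4 and 5, and add the adverse-event check to visit 6.
- In 7.6, remove the footnote mark from the adverse-event row at weeks 8 and 12 and mark week 24. The footnote can stay on the treatment and compliance rows.
- Amend the flow chart so that weeks 8, 12 and 24 match.
- Amend 9.1 so that off-device events up to week 24 count as adverse events.
- In 11.3, state that events will be reported separately for on-device and off-device time, each with its participant-weeks.

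The cost is a protocol amendment and perhaps one or two minutes (an estimate) in calls already scheduled. Contacts rise from 240–480 to 600. The week 24 question would rely on 12 weeks of recall. More background events will be recorded, and with no control arm they will be hard to attribute once high-intensity therapy or GP-prescribed drugs have started. Separate reporting makes that limit visible but does not remove it.
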